## STUDY SYNOPSIS

Sponsor / Sponsor- Investigator	PD Dr. med. [name]
Study Title:	Effects of photodynamic therapy on the human inguinal skin microbiome to improve antiseptic Effect – pilot 2
Short Title / Study ID:	Effects of photodynamic therapy on skin microbiome (PHOMIC-II)
Protocol Version and Date:	v04, 27.11.2020
Trial registration:	Bundesamtes für Gesundheit: www.kofam.ch . SNCTP  International trial registry ClinicalTrials.gov ( clinicaltrials.gov ) NCT04618276
Study category and Rationale	Other clinical study Category A
Background and Rationale:	Periprosthetic joint infections are a feared complication after orthopedic surgery in particular in our increasing elderly population. These infections are usually difficult to treat, because microorganisms persist in biofilms on the orthopedic implant surface. Therefore, it would be desirable to prevent these infections. It is hypothesized that bacteria from the skin surface or dermis - such as Staphylococcus aureus , coagulase-negative staphylococci, or Cutibacterium sp. - are transmitted into the periimplant tissue during surgery. In an ongoing interdisciplinary study with the Orthopedic University Hospital Balgrist (data in preparation for publication), we see that common skin antisepsis preparation is not effective to eliminate skin bacteria before surgery because they persist in sebaceous or sweat glands. Photodynamic therapy (PDT) has recently gained attention in the treatment of acne, a disease of the pilosebaceous unit, in which also Cutibacterium acnes is implicated. The PDT works here on the one hand through a long-lasting destruction of the sebaceous glands, and on the other hand due to anti-inflammatory and antimicrobial effects.
Objective(s):	The overarching aim of this research project is to prevent orthopedic implant-associated infections. This study aims to investigate if PDT has an effect on bacterial skin colonization in order to improve skin antisepsis strategies for the prevention of surgical site infections.  In a previous pilot study, we investigated if skin antisepsis is improved with previous PDT with the photosensitizer-inducing prodrug 5% topical methyl aminolevulinate (MAL) on inguinal skin in 10 participants. The induced photosensitizer was protoporphyrin IX (Pp IX, 635 nm) activated by red light. We showed a complete sterilization of colonizing skin bacteria at the same day after this treatment. However, orthopedic surgeons are hesitant to perform an arthroplasty surgery after such a treatment due to skin erythema for a few days.  We are entirely convinced about this novel prevention concept but need to identify the photosensitizer with the ideal balance of bactericidal effect versus skin irritation. Building upon the data we gathered, we will explore PDT with the two photosensitizers MAL and Methylene blue with potentially less local side-effects (skin erythema).

Outcome(s):	
Primary outcome:  Effect of photodynamic treatment with the photosensitizers Pp IX (MAL) and Methylene blue in combination with surgical antisepsis on bacterial skin colonization on the day of application and on day 1, 3, and 5
 
Secondary outcome:  Effect of PDT on the skin microbiome using molecular techniques.

Study design:	Pilot study, open label, single center
Inclusion / Exclusion criteria:	
Inclusion criteria  Healthy male and female participants <math>\geq 18</math> years who
 
 
volunteer for the pilot study in which a routine photodynamic treatment in the Department of Dermatology will be applied and effect of skin colonization will be analyzed, and
 
an informed consent is signed by the participant (after information about the project).
 
 
Exclusion criteria
 
 
Pregnant and lacting women
 
Participants with inability to follow the procedures of the study, e.g. due to language problems, psychological disorders, dementia, etc.,
 
Participants taking antibiotics in the 14 days prior to PDT or until follow-up at 21 days
 
Participants who received oral retinoid therapy within the last 6 months
 
Participants who received anti-inflammatory agents as NSAR within the 14 days prior and after the PDT
 
Participants taking any photosensitizing drugs within 4 weeks prior to PDT
 
Participants who had a history of photosensitivity disorder
 
Fitzpatrick's skin phototype V-VI
 

Study Intervention:	
 
Photosensitizer application, followed by PDT (1x)
 
Skin swabs on day 0, 1, 3, and 5
 
 
Group A: use of MAL induced Pp IX photosensitizer  Group B: use of Methylene blue photosensitizer

Reference Intervention:	Skin swabs before and after skin antisepsis in 10 participants without PDT from the contralateral side.
Number of Participants with Rationale:	Aim: 10 volunteers in group A and 10 volunteers in group B There will be only descriptive statistics to see if numbers of colonizing bacteria are decreased with PDT to plan a clinical trial in patients getting a hip joint arthroplasty and previous antisepsis.
Study Duration:	1 year
Study Schedule:	
 
Project start (FPFV): January 2021 
 
First participant: January 2021
 
Last participant: June 2021
 
 
 
Project end (LPLV): December 2021
 

Investigator(s):	[name] Division of Infectious Diseases and Hospital Hygiene University Hospital Zurich [name] Email: [contact] [contact]
Study Centre(s):	Single-center
Statistical Considerations:	Categorical data will be tested for differences using Fisher's exact or chi-squared tests, as appropriate, whereas continuous variables will be tested using Wilcoxon rank sum tests.
GCP Statement:	This study will be conducted in compliance with the protocol, the current version of the Declaration of Helsinki, the ICH-GCP as well as all national legal and regulatory requirements.

## LIST OF ABBREVIATIONS

AE	Adverse Event
ClinO	Clinical Trial Ordinance (KlinV)
CRF	Case Report Form
eCRF	Electronic Case Report Form
GCP	Good Clinical Practice
ICH	International Council on Harmonization
ISF	Investigator Site File
PI	Principal Investigator
SAE	Serious Adverse Event
SDV	Source Data Verification
SNCTP	Swiss National Clinical Trial Portal
SOP	Standard Operating Procedure
TMF	Trial Master File
PJI	Periprosthetic Joint Infection
C. avidum	Cutibacterium avidum
CNS	Cogulase-negative staphylococci
Sp.	Species
CEC	Competent Ethics Committee
PDT	Photodynamic therapy
MAL	Methyl aminolevulinate
NSAR	Non-steroidal anti-inflammatory drugs
Pp IX	Protoporphyrin IX

## 1.5 Monitoring Institution

Since we only measure microbiological data from skin samples, we think, that intern monitoring would be adequate. See chapter 12.3.

# ETHICAL AND REGULATOR ASPECTS

Before this study will be conducted, the protocol, the proposed participant information and consent form as well as other study-specific documents will be submitted to a properly constituted Competent Ethics Committee (CEC) in agreement with local legal requirements, for formal approval.

The decision of the CEC concerning the conduct of the study will be made in writing to the Sponsor-Investigator before commencement of this study. The clinical study can only begin once approval from the CEC has been received.

## 1.6 Study Registration

The study will be registered at the Swiss National Clinical Trials Portal (SNCTP) and in the international trial registry ClinicalTrials.gov ([clinicaltrials.gov](http://clinicaltrials.gov)).

## **1.7 Categorization of the Study**

**Category A:** The health-related study intervention (PDT) entails only minimal risks and burdens.

## **1.8 Competent Ethics Committee (CEC)**

Approval from the appropriate constituted Competent Ethics Committee is sought for the clinical trial. The reporting duties and allowed time frame are respected. No substantial amendments are made to the protocol without prior CEC approval, except where necessary to eliminate apparent immediate hazards to study participants. Premature study end or interruption of the study is reported within 15 days. The regular end of the study is reported to the CEC within 90 days, the final study report shall be submitted within one year after study end. Amendments are reported according to chapter 2.9.

## **1.9 Ethical Conduct of the Study**

The study will be carried out in accordance with principles enunciated in the current version of the Declaration of Helsinki, the guidelines of Good Clinical Practice (GCP) issued by ICH, and Swiss competent authority's requirements.

CEC will receive annual safety and interim reports and be informed about non-substantial amendments, the course of the study, and the study stop/ end in agreement with local requirements.

## **1.10 Declaration of Interest**

No conflict of interest

## **1.11 Participant Information and Informed Consent**

The investigator must explain to each Participant the nature of the study, its purpose, the procedures involved, the expected duration, the potential risks and benefits and any discomfort it may entail. Each participant must be informed that the participation in the study is voluntary and that he/she may withdraw from the study at any time and that withdrawal of consent will not affect his/her subsequent medical treatment.

The participant must be informed that his/her medical records may be examined by authorized individuals other than their treating physician.

All participants for this study will be provided a participant information sheet and a consent form describing this study and providing sufficient information for participants to make an informed decision about their participation in this study.

The participant information sheet and the consent form will be submitted with the protocol for review and approval for the study by the CEC. The formal consent of a participant, using the approved consent form, must be obtained before that participant is submitted to any study procedure.

The participant should read and consider the statement before signing and dating the informed consent form, and should be given a copy of the signed document. The consent form must also be signed and dated by the investigator (or his designee) and it will be retained as part of the study records.

## **1.12 Participant Privacy and Confidentiality**

The investigators are liable to treat the entire information related to the study and the compiled data strictly confidentially. Any passing-on of information to persons that are not directly involved in the study must be approved by the owner of the information.

Data generation, transmission, archiving and analysis of personal data within this study, strictly follows the current Swiss legal requirements for data protection. Prerequisite is the voluntary

approval of the Participant given by signing the informed consent prior start of participation of the clinical trial.

Individual participant medical information obtained as a result of this study is considered confidential and disclosure to third parties is prohibited. Participant's confidentiality will be further ensured by utilizing participant identification code numbers to correspond to treatment data in the computer files.

Such medical information may be given to the participant's personal physician or to other appropriate medical personnel responsible for the participant's welfare, if the patient has given his/her written consent to do so.

Data generated as a result of this study are to be available for inspection on request by the monitors and by the CEC.

### **1.13 Early Termination of the Study**

The Sponsor-Investigator may discontinue the study prematurely according to certain circumstances:

- ethical concerns,
- insufficient participant recruitment,
- when the safety of the participants is doubtful or at risk, respectively,
- alterations in accepted clinical practice that make the continuation of a clinical trial unwise,
- early evidence of benefit or harm of the experimental intervention

### **1.14 Protocol Amendments**

Substantial amendments (significant changes) are only implemented after approval of the CEC.

Significant changes to be authorized by the CEC are the following:

- changes affecting the participants' safety and health, or their rights and obligations;
- changes to the protocol, and in particular changes based on new scientific knowledge which concern the trial design, the method of investigation, the endpoints or the form of statistical analysis;
- a change of trial site, or conducting the clinical trial at an additional site; or
- a change of sponsor, coordinating investigator or investigator responsible at a trial site.

Under emergency circumstances, deviations from the protocol to protect the rights, safety and well-being of human participants may proceed without prior approval of the sponsor and the CEC. Such deviations shall be documented and reported to the sponsor and the CEC as soon as possible.

All Non-substantial amendments are communicated to the CEC within the Annual Safety Report (ASR).

## **2 INTRODUCTION**

### **2.1 Background and Rationale**

The use of orthopedic implants has been steadily increasing over the last 50 years. Despite considerable technical progress, including perioperative skin disinfection and antibiotic prophylaxis, implant-associated infections remain a feared complication. Infection rates up to 2% after primary joint arthroplasties (Tande and Patel 2014) have been described. National data published by Swissnoso – the National Center for Infection Prevention –reported an infection rate of 1.2% in hip arthroplasties (Vergleichsbericht 2015/2016). Considering an infection rate of up to 1.2%, 400 surgeries with primary hip arthroplasty implantation at the Orthopedic Department of the Balgrist University Hospital (data of 2015) would result in five periprosthetic joint infections

(PJI) per year, which is medically highly relevant regarding morbidity, mortality and estimated costs of 225'000 CHF in total.

Because bacteria grow and persist in biofilms on the implant surface such infections are difficult to eradicate. Definite cure of biofilm infections requires adequate surgical debridement and prolonged treatment with an antimicrobial agent resulting in high health-care costs (Tande and Patel 2014). Most commonly isolated microorganisms in implant-associated infections are staphylococci, streptococci, enterococci, Gram-negative bacteria, and anaerobic bacteria such as *Cutibacterium acnes/avidum* (formerly *Propionibacterium acnes/avidum*) (Tande and Patel 2014).

The majority of implant-associated infections are acquired during surgery. It is hypothesized that the same bacteria that colonize the skin surface contaminate the orthopedic implant and cause acute or chronic infections (Pulido, Ghanem et al. 2008). Prevention of implant-associated infections is key to avoid re-operations and prolonged antibiotic treatment. Current preoperative prevention strategies are multifaceted with the focus on skin antisepsis and single shot of an antibiotic within 30-60 minutes before surgery (Bratzler, Dellinger et al. 2013, Dumville, McFarlane et al. 2015). Preoperative skin antisepsis is performed with alcoholic povidone-iodine (PVI) or chlorhexidine gluconate (CHG) prior to implantation as a standard skin preparation (Dumville, McFarlane et al. 2013, Berrios-Torres, Umscheid et al. 2017). Povidone iodine oxidizes cell constituents and inactivates proteins by iodinating them. Regarding the skin commensal *Cutibacterium acnes*, it could be shown that despite administration of standard preoperative prophylaxis before shoulder arthroplasty surgeries, *C. acnes* could be detected in different sample types (in dermis, fascia, synovium, and glenoid tissue of shoulder) of 3 out of 10 patients without any signs of infection (Matsen, Russ et al. 2015). There is an increasing number of studies reporting the presence of bacteria in deep tissue, which is commonly considered as sterile. A recent study by Lee et al. found viable *C. acnes* in the dermal tissue in seven out of 10 male volunteers after surface skin antisepsis (Lee, Pottinger et al. 2014). All these study results have led to the assumption that not only the superficial skin bacteria but also bacteria in the dermis may find the way to deeper structures and infect an implant.

We hypothesize that local PDT is able to reduce persistent skin colonizing bacteria through the destruction of the sebaceous and sweat glands as well through bactericidal effects and thus improve skin antisepsis before surgical incision and implantation of foreign material leading to a lower rate of surgical site infections.

In a previous pilot study, we investigated if skin antisepsis is improved with previous PDT with the photosensitizer- inducing prodrug 5% topical methyl aminolevulinate (MAL) on inguinal skin in 10 participants. The induced photosensitizer was protoporphyrin IX (inducing a photodynamic effect with 635 nm light source) and we showed a complete sterilization of colonizing skin bacteria after this treatment (Waldmann, Schmid et al. 2020). However, due to skin erythema for a few days after PDT, orthopedic surgeons would be hesitant to perform an arthroplasty surgery after this treatment. Therefore, we aim to have a PDT with less local side-effects (skin erythema).

Ondine's methylene blue based photosensitizer NF-031 is mainly formulated in a primarily hydrophilic carrier, and therefore does not penetrate the stratum corneum over short periods of time, providing potent surface disinfection. According to the company Ondine, we can expect less side effects as with Pp IX. We will also repeat the MAL PDT with day light as a promising light source with expected less side effects such as pain and redness (Wiegell, Haedersdal et al. 2008, Rubel, Spelman et al. 2014).

The aim of this pilot study is to evaluate the effect of PDT with the photosensitizer MAL with and the photosensitizer Methylene blue on colonizing bacteria immediately before surgical skin antisepsis and after it. If we see promising results in this pilot study, we will plan a prospective clinical trial in patients undergoing hip arthroplasty surgery.

## 2.2 Study Intervention and Indication

Study intervention	Indication
PDT  - Photosensitizer in group A: MAL - photosensitizer in group B: methylene blue	
 
- Bactericidal effect on skin bacteria (skin sterility)
 

Skin swabs	
 
- Skin scraping method
 
- Measurement of bacterial growth of colonizing bacteria and quantitative bacterial changes using molecular methods
 

## 2.3 Clinical Evidence to Date

PDT has recently gained attention in the treatment of acne, a disease of the pilosebaceous unit, in which also *C. acnes* is implicated. The PDT works here on the one hand through a long lasting destruction of the sebaceous glands, and on the other hand due to anti-inflammatory and antimicrobial effects (Sakamoto, Lopes et al. 2010). In following studies, photodynamic therapy not only validated its efficient activity against bacteria involved in acne such as *C. acnes*, it showed also activity against various other classes of microorganisms (Awad, Tovmasyan et al. 2016). The mechanism of action of PDT is a photochemical reaction through the generation of reactive oxygen species in the presence of oxygen, mainly excited singlet oxygen, by a non-toxic photosensitizer reacting with visible light. PDT is routinely performed among others for non-melanoma skin cancer and therapy-refractory inflammatory dermatoses at the Department of Dermatology at the University Hospital Zurich. The treatment enjoys great popularity as it is well tolerated, can be repeated arbitrarily often, and gives excellent cosmetic results.

In a previous pilot study, we investigated if skin antisepsis is improved with previous PDT with the photosensitizer- inducing prodrug 5% topical methyl aminolevulinate (MAL) on inguinal skin in 10 participants. The induced photosensitizer was protoporphyrin IX (inducing a photodynamic effect with 635 nm light source) and we showed a complete sterilization of colonizing skin bacteria after this treatment (Waldmann, Schmid et al. 2020). However, due to skin erythema for a few days after PDT, orthopedic surgeons would be hesitant to perform an arthroplasty surgery after this treatment. Therefore, we aim to have a PDT with less local side-effects (skin erythema).

## 2.4 Justification of Study Intervention

PDT enjoys great popularity as it is well tolerated. Therefore, we select this promising treatment to investigate an innovative strategy to improve skin antisepsis in a pilot study. If we see that we have sterile cultures after PDT and skin antisepsis without side effects, we will plan a larger prospective study based on these data.

## 2.5 Explanation for Choice of Comparator Intervention

We will use for our control group without PDT the contralateral groin of the same participants (no further participants needed).

## 2.6 Risk / Benefits

In the following, we describe benefits, weakness, opportunities, and risks of this study.

**Benefits**

- Important topic in our society of more elderly patients with the increasing need of orthopedic implants
- PDT is a promising method for improving skin antisepsis
- established network with infectious diseases specialists (Lead), microbiologists, dermatologists, and orthopedic surgeons

**Weakness**

- not applicable

**Opportunities**

- Improved skin antisepsis by PDT would change routine praxis in orthopedic surgery as well as overall in surgery with the consequent reduction in morbidity, mortality, and health-care costs

**Risks**

- Minimal risk (transient erythema and pain) using PDT (no long-term sequelae). No inflammation seen on histopathology in previous trial

Possible side effects of the PDT are pain in the area of treatment, erythema and edema during and after light treatment (Borgia, Giuffrida et al. 2018). These side effects are self-limiting. We expect less erythema with day-light PDT and with the photosensitizer Methylene blue than with the previously tested MAL induced Pp IX photosensitizer (Waldmann, Schmid et al. 2020).

Since our study interventions (see above) have minimal risks for participants, it is reasonable to conduct this pilot study before starting a larger clinical trial with patients undergoing hip arthroplasty surgery.

## 2.7 Study Population

Twenty healthy male and female volunteers'  $\geq 18$  years will be recruited for this clinical study. The first ten enrolled participants will be allocated to receive MAL (group A), the other ten participants will receive Methylene blue (group B). The type of PDT (group A and B) is not blinded to both participant and study investigator. The study will be approved by the local ethical committee and conducted with a study nurse and a doctoral thesis student (to be determined) in collaboration with the Clinic for Dermatology at the University Hospital Zurich, and with the Institute of Medical Microbiology at the University of Zurich. An informed consent will be obtained from each participant. We will exclude pregnant and lactating women, participants taking antibiotics in the 14 days prior to the PDT or until follow-up at 21 days, participants who received oral retinoid therapy within the last 6 months, participants who received anti-inflammatory agents within the 14 days prior and after the photodynamic treatment, participants taking any photosensitizing drugs within 4 weeks prior to the photodynamic treatment, participants who had a history of photosensitivity disorder or having a Fitzpatrick's skin phototype V-V (16).

We will not include vulnerable participants. There will be a financial compensation (value CHF 50.00) to the participants as in the previous trial (PHOMIC) was asked by the ethical committee.

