## **4 STUDY OUTCOMES**

### **4.1 Primary Outcome**

Effect of PDT with the MAL-induced Pp IX (group A) and Methylene blue (Ondine NF-031) (group B) in combination with skin antisepsis on bacterial skin colonization on the day of application and on day 0, 1, 3 and 5

- 1.1. To quantitatively evaluate bacterial density and species before and after PDT and skin antisepsis using culture techniques

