## **5 STUDY DESIGN AND COURSE OF STUDY**

### **5.1 General Study Design and Justification of the Design**

This is a pilot study of healthy volunteers, open label, and single center. We will use a parallel assignment of Arm A and B without masking (open label). Allocation is non-randomized, we will start with group A, followed by group B.

If we see promising results, we will plan a prospective clinical trial in patients undergoing hip arthroplasty surgery.

[figure not shown]
The intended procedures are PDT on the first day followed by skin swabbing for control of skin microbiome of treated area immediately after PDT (day 0) and after 1, 3 and 5 days of PDT to analyze how long the effect lasts.

We think that this study design with healthy volunteers is adequate before starting a clinical trial.

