## Microbiology

In short, the patient's sample swabs will be streaked out onto Columbia sheep blood agar plate without antibiotics (bioMérieux, Marly-l'Etoile, France), colistin-nalidixic acid (CNA) blood agar (bioMérieux) plate for aerobic cultivation and a Brucella plate (in-house sheep blood agar plates with hemin and vitamin K1) for anaerobic cultivation using GENbag (bioMérieux). Final identification will be done by matrix-assisted laser desorption ionization-time of flight mass spectrometry spectrometry (MALDI-TOF MS) using a Bruker MALDI Biotyper. The amount of bacteria will be semiquantitative described as +, ++, +++ based on growth on agar plates. All cultured microorganisms will be stored in skim milk at -80C° for potential subsequent analysis by whole genome sequencing for analyzing the secondary outcome.

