## **12.2 Data Management**

All basic demographic data, all microbiological and histopathological results will be manually entered in an automatically secured online processing system (REDCap® electronic data capture system). The PI will check and validate data on a regular basis for consistency.

All study data are encrypted in REDCap®. The principal investigator is responsible for data collection and will keep the screening log, which guarantees the confidentiality of data by the use of participant ID numbers. The participant ID numbers are automatically assigned in consecutive ascending form by the REDCap® system. For the purpose of fulfilling their task, the principal investigator grants the necessary access authorization in the form of user log-in and password to the study staff. Thus, the data cannot be altered in any way by unauthorized persons. In the REDCap® system, all relevant processing operations are documented in a user-specific manner in order to ensure traceability. This is done by means of registration software, which records who has edited which data at which time.

All patients have to give their written consent to the project. These informed consents documents (IC) will be stored according to ethical regulations.

Health related personal data captured during this project from participants are strictly confidential and disclosure to third parties is prohibited; coding will safeguard participants' confidentiality. Confidentiality will be ensured by using coded data. The code will be protected against unauthorized access and will be stored appropriately. Data will be stored for up to 10 years after publishing the study as requested by most journals.

- Patient's and microbiological data:

- [name] will be responsible for basic characteristics of the volunteers of this pilot study. After the last study visit, data will be encoded by the PI and safely stored at the Investigator Site File.
- Clinical and microbiological data will be saved in the electronical database Redcap (see above)
- The collected project data may be subject to inspection by the CEC.

- *Handling of isolated bacteria of the scrapped skin samples:*  

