The sub-cultivated bacterial samples will be stored and labeled with an encoded name at -80°C at the bacteriology laboratory of the Division of Infectious Diseases and Hospital Epidemiology (responsible [name]). The code for the bacterial strains with correspondence to patient data will be stored at the Investigator Site File.

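### Masked reading of the culture plates is not specified, although the density part of the primary outcome is a judged +/++/+++ grade without cut-points

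*Combined protocol and SAP*

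**What the plan says.** All references are to the combined protocol and SAP.

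- **Outcome.** Section 4.1 sets the aim: "To quantitatively evaluate bacterial density and species before and after PDT and skin antisepsis using culture techniques". Section 8.2.1 (Microbiology) turns density into a grade: "The amount of bacteria will be semiquantitative described as +, ++, +++ based on growth on agar plates". It gives no colony count, grade boundary or duplicate reading. Species is handled by instrument: "Final identification will be done by matrix-assisted laser desorption ionization-time of flight mass spectrometry spectrometry (MALDI-TOF MS) using a Bruker MALDI Biotyper".
- **Masking.** Section 5.1: "We will use a parallel assignment of Arm A and B without masking (open label". Section 2.7: "The type of PDT (group A and B) is not blinded to both participant and study investigator". Section 5.3 lists selection and representativeness only.
- **Allocation and identifiers.** Section 5.1: "Allocation is non-randomized, we will start with group A, followed by group B". Section 12.2: "The participant ID numbers are automatically assigned in consecutive ascending form by the REDCap® system". Sections 5.2, 8.1 and 8.3.2 place PDT in the right groin; the other groin is the control (2.5, 5.2).
- **Coding of material.** Section 12.2 says the sub-cultivated isolates are "stored and labeled with an encoded name", and section 12.6 says much the same of stored biological material.
- **Checks.** Section 12.3 provides for regular control of results by a microbiologist outside the study, still to be chosen.

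**The concern.** Participants and the operator cannot readily be masked to a light treatment. The plate reader can be, because section 8.3.2 sends the swabs to a microbiology laboratory. Where growth is judged by eye without fixed boundaries, borderline plates can be graded either way. A reader who knows which plate comes from the treated groin, or was taken after treatment, may grade those plates lower without intending to. The protocol records a strong prior belief in the concept (synopsis and 3.2), so the likely direction is towards PDT.

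At stake is the descriptive contrast between treated and control groin and between before and after. Section 10.3.2 makes a descriptive before/after comparison the primary analysis. Sections 2.1 and 5.1 make a trial in hip arthroplasty patients depend on promising results here.

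**Working it through.** The plan states no effect size, variance or power, so there is no figure to reproduce. The check is first textual, then a simple illustration.

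**1. Is the reader masked anywhere?** Section 5.1 says there is no masking. Section 2.7 names participant and investigator but not the laboratory. Sections 5.3, 8.2.1, 8.3.2 and 12.3 do not mention masked reading. Masking of the reader is therefore not specified.

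**2. Would the existing coding mask the reader anyway?** Not on what is written.

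- The encoded names in 12.2 and 12.6 are for stored isolates and stored material. Nothing is said about the label on a swab or plate when it is graded.
- PDT is always on the right, so a side on the label would identify the treated groin.
- Participant numbers run consecutively and group A is enrolled before group B, so number order would reveal the arm.
- The outside microbiologist in 12.3 is not described as masked.

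**3. Illustrative size, no true effect.** Let *g* be the share of plates with growth and *d* the share of growing PDT plates graded one step too low. The mean shift is *g* × *d* × 1 grade. Both inputs are assumptions.

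| *g* | *d* = 20% | *d* = 30% | *d* = 40% |
|---|---|---|---|
| 50% | 0.10 | 0.15 | 0.20 |
| 70% | 0.14 | 0.21 | 0.28 |
| 80% | 0.16 | 0.24 | 0.32 |

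For *g* = 70%, take assumed grades 0/1/2/3 in 30/30/25/15% of plates. The mean is 0.30 × 1 + 0.25 × 2 + 0.15 × 3 = 1.25. The apparent reduction is then 0.14/1.25 = 11% to 0.28/1.25 = 22%. If few plates grow after antisepsis, *g* is smaller and so is the shift.

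**4. Effect on the planned rank-sum test.** This used 4,000 simulated trials per setting, four equally likely grades (so *g* = 75%), the two groins treated as independent as the planned test does, and no true effect. Share with p < 0.05:

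| Share downgraded | 10 vs 10 | 20 vs 20 |
|---|---|---|
| 0% | 5.1% | 5.1% |
| 20% | 5.0% | 7.0% |
| 30% | 7.2% | 9.7% |
| 50% | 9.7% | 18.6% |

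The simulated shifts at 10 vs 10 (0.15, 0.23 and 0.37 grade at 20, 30 and 50%) agree with 0.75 × *d* to within simulation error. Both sizes are shown because section 5.2 takes control swabs from all participants, while section 7.1.2 takes them from the first 10.

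**The case against.** The strongest reply is that this is a 20-volunteer, mainly descriptive pilot. An independent laboratory may already read coded samples, and the result that matters is hard to misread.

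Much of this stands:

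- **Only part of the primary outcome is a judged grade.** Species comes from mass spectrometry. Section 2.4 ties the larger study to sterile cultures, which is growth/no growth. Calling a growing plate sterile would also conflict with the plan in 8.2.1 to identify organisms and store everything cultured. Frozen remainders and later PCR (8.1, 8.2.2) offer a partial check.
- **Section 12.3 does plan an outside check**, and the cultures are the Institute of Medical Microbiology's task (section 13). The separation is incomplete, since section 13 also gives the sponsor's division a part in generating the microbiological data.
- **Significance is little affected at 10 versus 10** for moderate misgrading.

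A reader might infer that the plate reader knows the allocation, or that samples are coded only for privacy. The documents support neither: they do not say what the swab label or request form shows, and they give no purpose for the encoded names. Nor does the sentence in 2.7 show that the laboratory is unmasked; it concerns the type of PDT and two other parties.

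The descriptive aim does not remove the problem, because the descriptive shift is what differential grading moves. If the laboratory already works masked, the plan needs only to say so.

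**Conclusion.** The point holds as an unaddressed risk of bias in the density grade. It is not evidence that the reader is unmasked or that a bias of known size will occur. The grade has no stated boundaries, the design is declared unmasked, and no stated safeguard hides side, visit or before/after status from the person grading.

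The 0.14–0.28 grade figure rests wholly on the assumed 70% growth rate and 20–40% downgrading. It shows the direction and a possible order of size. A reader might also infer that false-positive p-values are the main harm. At 10 versus 10 the calculation does not support that: rejection stays at about 5% with 20% downgrading and reaches 7.2% with 30%. The rise is larger at 20 versus 20. The main exposure is the descriptive contrast carried into the next trial. The change is worth making before the first swab, because grades already read without masking cannot be made masked afterwards.

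**What to change.** Add to sections 5.3 and 8.2.1:

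1. Each swab and plate carries only a random sample number, with no side, visit, before/after status, arm or consecutive participant number.
2. The existing laboratory staff grade the plates without the key, against cut-points for 0, +, ++ and +++ written down beforehand.
3. The key is held outside the laboratory and opened only after the grades are locked in REDCap.

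State two limits alongside. Because group A is run before group B, receipt date may still reveal the arm, so the masking protects mainly the within-participant side and before/after comparisons. It also does not remove bias from scraping, which is done unmasked.

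The cost is maintaining a label list and key and agreeing the cut-points. No extra reader, visit, participant or sample is needed.
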